5.3. Safety Analysis Set

The safety analysis set will include all subjects who are enrolled (randomized) and received at least 1 dose of double-blind medication.

5.4. Other Analysis Sets

No other analysis sets are defined for this study.

5.5. Treatment Misallocations

For subjects, who were not treated, not randomized, or received incorrect treatment, the following rules will be used:

- Randomized but not treated, then they will be excluded from the ITT and PP analysis sets for efficacy evaluations and excluded from the safety analyses as actual treatment is missing.
- Treated but not randomized, then by definition they will be excluded from the efficacy analyses since randomized treatment is missing, but will be reported under the treatment they actually received for all safety analyses.
- Randomized but took incorrect treatment, then they will be reported under their randomized treatment group for all efficacy analyses, but will reported under the treatment they actually received for all safety analyses.

5.6. Protocol Deviations

Below are the protocol deviations that relate to the “Per-Protocol Analysis Set” (Section 5.2).

5.6.1. Deviations Assessed Prior to Randomization

A protocol deviator is a subject who was wrongly enrolled into the study, when inclusion or exclusion criteria were not appropriately satisfied. See [Protocol, Section 4](#).

5.6.2. Deviations Assessed Post-Randomization

Protocol deviations include but are not limited to the following:

- Violations on concomitant medications (see [protocol Section 5.5](#));

- Lack of dosing adherence (level to be defined case by case);
- Dosing errors (eg, treatment misallocation, see [Section 5.5](#) in this SAP);
- Use of diflunisal, tauroursodeoxycholate, and doxycycline during the study.

A full list of protocol deviations will be compiled for the study report prior to database closure. All deviations will be reviewed and a determination of which data to include in the Per-Protocol Analysis Set will be made prior to unblinding the study database.

6. ENDPOINTS AND COVARIATES

6.1. Efficacy Endpoint(s)

6.1.1. Primary Efficacy Endpoint(s)

The primary analysis uses a hierarchical combination applying the method of Finkelstein-Schoenfeld ([Finkelstein 1999](#)) to:

- *All-cause mortality, and*
- *Frequency of cardiovascular-related hospitalizations over the duration of the trial, which is defined as the number of times a subject is hospitalized (ie, admitted to a hospital) for cardiovascular-related morbidity.*

6.1.2. Key Secondary Efficacy Endpoint(s)

- 1. Change from Baseline to Month 30 in the distance walked during 6-Minute Walk Test (6MWT),*
- 2. Change from Baseline to Month 30 in the Kansas City Cardiomyopathy Questionnaire Overall Score (KCCQ-OS).*

6.1.3. Secondary Endpoints

- 1. Cardiovascular-related mortality,*
- 2. Frequency of cardiovascular-related hospitalization,*
- 3. All-cause mortality,*
- 4. TTR stabilization at Month 1.*

6.1.4. Exploratory Endpoints

- *Frequency of all-cause hospitalization,*
- *Cardiovascular-related days hospitalized,*
- *All-cause days hospitalized,*

- *All-cause mortality and the frequency of all-cause hospitalization using the Finkelstein-Schoenfeld analysis,*
- *All-cause mortality and cardiovascular-related days hospitalized using the Finkelstein-Schoenfeld analysis,*
- *Cardiovascular-related mortality and frequency of cardiovascular-related hospitalization using the Finkelstein-Schoenfeld analysis,*
- *TTR stabilization at each time points other than Month 1,*
- *TTR concentration at each time point, Change from baseline at time points other than Month 30 in the 6-Minute Walk Test (6MWT),*
- *Change from baseline at time points other than Month 30 in the Kansas City Cardiomyopathy Questionnaire Overall Score (KCCQ-OS),*
- *Change from baseline at each time point in Kansas City Cardiomyopathy Questionnaire: (KCCQ) domain scores (Physical limitation, Symptom stability, Symptom frequency, Symptom burden, Total symptom, Self-efficacy, Social limitation, and Quality of life) and Clinical summary score,*
- *Change from Baseline at each time point in EuroQoL-5 Dimensions (EQ-5D-3L) Index Score and visual analog scale (VAS) scores,*
- *Patient Global Assessment at each time point,*
- *New York Heart Association Classification (NYHA) at each time point,*
- *Change from Baseline at each time point in modified Body Mass Index,*
- *Change from Baseline at each time point in NT-proBNP concentration,*
- *TTR oligomer concentration at each time point,*
- *Change from Baseline at each time point in select echocardiographic parameters, including:*
 - *End-diastolic interventricular septal wall thickness (mm),*
 - *Left ventricle posterior wall thickness (mm),*
 - *Left ventricular ejection fraction (%),*
 - *Left ventricular stroke volume (mL).*
 - *Global Longitudinal Strain,*

- Basal Septal,
- Mid Septal,
- Apical Septal,
- Basal Lateral,
- Mid Lateral,
- Apical Lateral,
- *Circumferential strain basal global,*
- *Circumferential strain mid global,*
- *Circumferential strain apical global,*
- *Radial strain basal global,*
- *Radial strain mid global,*

Radial strain apical global. Additionally, the following echocardiographic parameters will also be measured:

- *Fractional shortening (%),*
- *Left atrial diameter, anterior-posterior (mm),*
- *Left atrial diameter, medio-lateral (mm),*
- *Left atrial diameter, superior-inferior (mm),*
- *Left ventricular end systolic diameter (mm),*
- *Left ventricular end systolic volume (mL),*
- *Left ventricular end-diastolic diameter (mm),*
- *Left ventricular end-diastolic volume (mL),*
- *Left ventricular mass (g),*
- *E/A Ratio,*
- *E/E' Ratio.*

6.2. Safety Endpoints

Safety and tolerability will be assessed with adverse event reporting as well as the conduct of ECGs, clinical laboratory testing, vital signs, and physical examinations.

6.3. Other Endpoints

Not Applicable.

6.4. Covariates

Baseline values will be included as a covariate in the analysis using the mixed model repeated measures (MMRM) model detailed in [Section 8.1.3](#). Where baseline scores are not available (or applicable) for the endpoints (eg, frequency of cardiovascular-related hospitalization), the NYHA baseline classification (NYHA Classes I and II combined and NYHA Class III) will be included in the appropriate models to address baseline severity levels.

All subjects who were incorrectly classified during randomization (wrong TTR Genotype or NYHA baseline classification) will be analyzed using the correct TTR Genotype or NYHA baseline classification values.

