10. Subject must have a Screening visit NT-proBNP concentration > 600 pg/mL (the conversion factor from conventional pg/mL to SI units is to divide by 8.45),
11. Subjects must be able to complete > 100 m on the 6-Minute Walk Test at Screening,

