8. Collect blood, and urine samples for the following clinical laboratories:
 - a. Hematology;
 - a. Serum Chemistry;
 - b. Coagulation (INR, PT);
 - c. Serology for Hepatitis B (HBsAg), Hepatitis C (anti-HCV), and HIV;
 - d. Serum and urine test for primary light chain amyloidosis (AL) [Section 7.6.8](#);
 - e. Urinalysis;
 - f. Genotyping - not needed for subjects with prior documented genotyping. In such instances, the original laboratory result, or copy will be filed as source documentation;
 - g. Urine pregnancy test – for women of childbearing potential.
9. Collect blood samples for NT-proBNP and troponin I.
10. Collect blood sample for diflunisal concentration ([Section 7.7.3](#)).

11. 6-Minute Walk Test ([Appendix 4](#)).
12. NYHA classification.
13. Documentation of prior medications.

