6.2.1. Baseline (Day 1)

Prior to dosing, the following procedures will be completed at the Baseline visit:

1. Review entrance criteria.
2. Randomization.
3. Medical history (updated for changes since Screening visit).
4. Brief Physical Examination with weight.
5. Single 12-lead ECG - prior to any blood pressure measurement or blood collection.
6. Vital signs (systolic and diastolic blood pressure supine and standing, pulse rate supine and standing, respiration rate, and body temperature).
7. Blood and urine sample collection for the following clinical laboratories:
 - a. Hematology;
 - b. Serum Chemistry;

- c. Coagulation (INR, PT);
 - d. Retinol Binding Protein;
 - e. Urinalysis;
 - f. Urine Pregnancy test – for women of childbearing potential.
8. Collect blood sample for TTR stabilization, TTR oligomer concentration, and TTR concentration assays pre-dose.
 9. Collect blood sample for diflunisal concentration ([Section 7.7.3](#)).
 10. Collect Baseline pre-dose blood sample as control for tafamidis concentration.
 11. Collect pharmacogenomic sample.
 12. Collect blood sample for NT-proBNP and troponin I.
 13. 6-Minute Walk Test ([Appendix 4](#)).
 14. Kansas City Cardiomyopathy Questionnaire ([Appendix 1.1](#)).
 15. EQ-5D-3L ([Appendix 2](#)).
 16. Patient Global Assessment ([Appendix 3](#)).
 17. NYHA classification.
 18. Documentation of concomitant medications.
 19. Adverse event reporting.
 20. Hospitalization determination.
 21. Documentation of vital status and transplant or cardiac mechanical assist device status.
 22. Dispense blinded medication.

Subjects will be instructed to take their first tafamidis daily dose of 4 capsules after the completion of the Baseline procedures and to continue dosing 4 capsules each day in the morning until the next study visit.

At the end of the visit, a time will be scheduled for the Week 2 phone call along with the Month 1 appointment. The subject will be instructed not to take their medication at home on the day of the Month 1 visit, but rather wait and take the medication when instructed by the site staff when they arrive at the clinic. A Subject Daily Dosing Diary stating the date and

time of the Month 1 visit will be issued to the subject. The subject will be reminded to return to the clinic with all dispensed study medication wallets.

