7.7.3. Diflunisal Concentration

After the recording of ECGs, Echocardiograms and blood pressure, a blood sample will be collected to determine if the subject has taken diflunisal. The blood sample for this assessment will be taken at Screening, Baseline and Months 1, 6, 18, and 30. Use of diflunisal during the study is not permitted. Subjects taking diflunisal will be appropriately counselled. Such subjects will be handled as protocol violators in the analysis as described in the Statistical Analysis Plan.

Samples will be analyzed using a validated analytical method in compliance with Pfizer standard operating procedures.

Detailed instructions for collection, storage, labeling, and shipment of all samples are provided in a separate study laboratory manual.

7.7.4. 6-Minute Walk Test (6MWT)

A 6MWT will be conducted during the Screening period and at the Baseline visit and at Month 6, 12, 18, 24, and 30 visits (or Early Study Discontinuation). There will be one 6MWT during the Screening period. Subjects who are unable to walk 100 meters at Screening will be considered a Screen Failure.

The test will be conducted in accordance with guidelines established by the American Thoracic Society.

Detailed instructions for conducting the 6MWT are provided in [Section Appendix 4](#).

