8.1.3. Mixed Model Repeated Measures (MMRM) Analyses

The endpoints evaluated at multiple time points will be analyzed *using a mixed model repeated measures ANCOVA (MMRM) with an unstructured covariance matrix (or as appropriate); center and subject-within-center as random effects; treatment, visit, TTR genotype (variant and wildtype), and visit-by-treatment interaction, as fixed effects and Baseline score as covariate.* While the NYHA baseline classification may serve as an indicator of baseline severity, the endpoints that are evaluated at baseline (and at multiple points post-baseline) will use their respective baseline scores as the appropriate covariate for the MMRM analysis described above.

For the analyses by TTR genotype, the same model specified above will be used, with the addition of terms for TTR genotype-by-treatment interaction and TTR genotype-by-treatment-by-visit 3-way interaction. Similarly for dose, the same model specified above will be used with replacement of “dose” for “treatment”. Appropriate CONTRAST statements will be used to generate the LSMEANS from the MMRM model (eg, for dose, 20 mg vs placebo and 80 mg vs placebo) at each post-baseline study visit. The subgroup analysis by NYHA baseline classification (NYHA Classes I and II combined and NYHA Class III) will be done using ANCOVA (MMRM) with an unstructured covariance matrix (or as appropriate); center and subject-within-center as random effects; treatment, visit, TTR genotype (variant and wildtype), NYHA baseline classification, visit-by-treatment interaction, NYHA baseline classification-by-treatment interaction, NYHA baseline classification-by-treatment-by-visit 3-way interaction as fixed effects and baseline score as covariate. All the subgroup analyses will be considered exploratory.

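### The Month 30 6MWT model uses one of the two pre-dose walks; adding the Screening walk would give a modest, nearly free gain in precision

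*SAP*

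**What the plan says.** - **Two walks before dosing.** Protocol 7.7.4: "A 6MWT will be conducted during the Screening period and at the Baseline visit and at Month 6, 12, 18, 24, and 30 visits", and "There will be one 6MWT during the Screening period". Protocol 6.2.1 lists the Day 1 walk among the procedures completed before the first dose.
- **The Screening walk decides entry.** Protocol 4.1, item 11: "Subjects must be able to complete > 100 m on the 6-Minute Walk Test at Screening". Every correctly enrolled subject should therefore have one.
- **One covariate in the model.** SAP 6.4: "Baseline values will be included as a covariate in the analysis using the mixed model repeated measures (MMRM) model". SAP 8.1.3 ends its model description "as fixed effects and Baseline score as covariate". The MODEL statement in SAP Appendix 1.3 has a single term, ybase.
- **Baseline is not defined for 6MWT.** The SAP spells out a baseline measurement only for vital signs (8.2.5). Screening and Baseline (Day 1) are separate visits throughout, so ybase is most naturally the Day 1 walk.
- **Testing order.** Under SAP 8.2.2, 6MWT at Month 30 is tested first after the primary analysis. KCCQ-OS can be declared significant only if 6MWT passes.
- **NT-proBNP** is also sampled at Screening ("Collect blood samples for NT-proBNP and troponin I", Protocol 6.1) and on Day 1 ("Collect blood sample for NT-proBNP and troponin I", Protocol 6.2.1). It is an exploratory endpoint (SAP 6.1.4).

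**The concern.** A single walk carries test-retest and day-to-day noise. As a covariate it therefore adjusts less well than the subject's underlying capacity would, and part of that noise stays in the residual variance of the Month 30 contrast. A second pre-dose walk recovers some of this. It is already collected and cannot be affected by treatment, yet no efficacy model uses it.

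What is at stake is the chance that 6MWT passes at 0.05 and, through the gate, the chance that KCCQ-OS can be claimed. Protocol 9.1 gives power only for the primary analysis, so the documents do not show how much margin the 6MWT test has.

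**Working it through.** **Plan's own figure.** There is none to reproduce. The documents give no SD, effect size, reliability, correlation or power for 6MWT.

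**Subjects at Month 30.** Allocation is 160 placebo and 240 pooled tafamidis (Protocol 3). Planning mortality is 25% and 12.5% (Protocol 9.1). Expected alive: 160 × 0.75 = 120 and 240 × 0.875 = 210, so 330 before other dropout.

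**Assumed quantities.** R is the reliability of one walk (0.80 to 0.95). r is the true-score correlation between baseline and Month 30 (0.6 to 0.9). The central case is R = 0.9, r = 0.8.

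**Exchangeable walks.** Residual variance, as a share of the total:

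- one walk: 1 − r²R²
- two walks: 1 − 2r²R²/(1 + R)

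Central case: one walk 1 − 0.64 × 0.81 = 0.4816. Two walks 1 − 0.64 × 1.62/1.9 = 0.4543. The ratio is 0.943, a cut of 5.7%.

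| Cut in residual variance | r = 0.6 | r = 0.7 | r = 0.8 | r = 0.9 |
|---|---|---|---|---|
| R = 0.80 | 3.3% | 5.1% | 7.7% | 12.0% |
| R = 0.90 | 2.2% | 3.5% | 5.7% | 10.0% |
| R = 0.95 | 1.2% | 2.0% | 3.5% | 7.0% |

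**Clinical state shifts between the visits.** Let c be the true-score correlation between Screening and Day 1, with Screening predicting Month 30 only through Day 1. Put a = rR, b = crR, p = cR. The explained share is (a² + b² − 2abp)/(1 − p²).

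- Central case, c = 0.95: a = 0.72, b = 0.684, p = 0.855. Explained share (0.5184 + 0.4679 − 0.8421)/0.2690 = 0.536. Ratio 0.4642/0.4816 = 0.964, a cut of 3.6%.
- Central case, c = 0.90: a cut of 2.5%.
- R = 0.95, r = 0.6: cuts of 0.6% (c = 0.95) and 0.4% (c = 0.90).
- If Screening adds nothing once Day 1 is known, the ratio is 1.00.

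**Planned model rather than single-visit ANCOVA.** The SAP model fits one baseline slope common to all five post-baseline visits, with unstructured covariance. With complete data, true-score correlation decaying smoothly over time and Screening one month before Day 1, the central cut is about 5% and the range 0.6 to 11.6%.

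**Subject equivalents, out of 330.** 330 × (1/0.943 − 1) is about 20 in the exchangeable central case.

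**Power.**

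- Starting from an assumed 80%: (1.960 + 0.842)/√0.943 − 1.960 = 0.925, which is 82.2%. The corners of the table give 80.5% and 84.8%.
- The only 6MWT contrast in the documents is −11 m against −44 m, a difference of 33 m, at 12 months in two unmatched studies (Protocol 1.2.1). With 120 and 210 subjects, SD 100 m (assumed) and observed correlation 0.6 to 0.7 between one pre-dose walk and Month 30, power is already 95.0 to 98.1% and rises by less than 1 point. With SD 120 m the gain reaches 2.5 points (92.0 to 94.5%).
- With a 20 m difference and SD 100 m (both assumed), power moves from 58.9 to 60.2% at one end (R = 0.9, observed correlation 0.6) and from 68.7 to 73.5% at the other (R = 0.8, observed correlation 0.7).

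**The case against.** **The plan is not wrong.** A single baseline covariate gives a valid test, and SAP 8.1.3 deliberately prefers each endpoint's own baseline score to NYHA class. This stands in full. A reader might infer bias or an analysis error; nothing in the documents supports that.

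**The walks may not be exchangeable.** Screening normally falls between Day −45 and Day −10 and can be extended by up to two weeks (Protocol 6.1). Diuretic doses may change in the four weeks before Baseline (5.8). Cardiovascular hospitalization is barred only in the last two weeks (4.1, item 8). This stands too. It is why the drift calculation is needed and why the lower end runs towards zero.

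**The upper end is a corner.** A 12% cut needs low reliability (0.80) together with a true-score correlation of 0.9 over 30 months in a progressive disease. At R = 0.9 and r of 0.6 to 0.7 the exchangeable cut is 2.2 to 3.5%.

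**A second covariate can lose subjects.** The repeated-measures models impute nothing (SAP 7), so a missing Screening walk would drop a subject from the alpha-controlled test. Wrongly enrolled subjects stay in ITT and leave only the per-protocol set (SAP 5.2, 5.6.1). A rule for missing values answers this, and it must be part of the change.

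**NT-proBNP and KCCQ-OS.** A reader might extend the stakes to both. NT-proBNP is exploratory and gates nothing. KCCQ-OS is first completed at Baseline (Protocol 7.7.1.1), so it has no Screening value and could benefit only through the gate.

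**Conclusion.** The point holds as an efficiency improvement to the 6MWT analysis. Two pre-dose walks are collected and the model uses one. Adding the second leaves the treatment contrast with the same meaning and cannot raise the large-sample residual variance.

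The gain is modest, and its size rests on the assumed R, r and c and, for power, on the assumed SD and effect. It should be quoted as a range with those assumptions attached, not as a loss that the plan can be shown to incur. Counting the saving against all 400 randomised subjects, which would give 24 in the central case, overstates it for a Month 30 contrast.

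**What to change.** Before unblinding, amend SAP 6.4, SAP 8.1.3 and the Appendix 1.3 code along these lines:

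- Baseline for 6MWT is the Day 1 pre-dose walk. Change from Baseline remains defined on that value.
- The Screening 6MWT distance is entered as a second covariate, beside the Day 1 value, in the 6MWT repeated-measures model, with a matching term in the MODEL statement.
- If the Screening walk was repeated, the last valid one is used.
- If it is missing, it is filled by a rule that ignores treatment, for example the prediction from the Day 1 walk, so that no ITT subject is lost.

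The same term may be added for NT-proBNP as an exploratory refinement. KCCQ-OS is unchanged.

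The cost is a few SAP sentences, one model term and one degree of freedom. No new visits, data or subjects are needed. A practice effect, or regression to the mean after threshold-based entry, is shared by both arms and is absorbed by the regression.

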7. HANDLING OF MISSING VALUES

No imputation will be done for missing cases for the primary analysis based on the Finkelstein-Schoenfeld method. A sensitivity analysis (of the primary) using multiple imputation as described in [Appendix 1.4](#) will be performed. Supplemental analyses of the two key secondary variables will group the subjects on the basis of their dropout or missing-data patterns using a pattern mixture model described in [Section 8.2.2](#). For all analyses using mixed model repeated measures, no imputation of missing values will be done.

8. STATISTICAL METHODOLOGY AND STATISTICAL ANALYSES

8.1. Statistical Methods

8.1.1. Finkelstein-Schoenfeld Analyses

The test is based on the principle that each subject in the clinical study is compared to every other subject within each stratum in a pair-wise manner. The method recognizes the higher importance of all-cause mortality. The pair-wise comparison proceeds in hierarchical fashion using all-cause mortality first, assigning a +1 to the “better” subject and a -1 to the “worse” subject ([Appendix 1.1](#)). A score, u_{ij} , represents the pair wise comparison and indicates whether patient i has the more favorable outcome than patient j. The “cardiovascular- related hospitalization” in all analyses, unless otherwise specified, will combine hospitalizations adjudicated as cardiovascular-related with hospitalizations adjudicated as indeterminate.

- *If both subjects are dead, then the subject with a longer survival time is assigned +1.*

- *If one subject is alive and the other is not, the live subject receives a +1 and the deceased one a -1.*
- *If both subjects are alive, the comparison uses cardiovascular-related hospitalization to assign scores. The subject with the fewer cardiovascular related hospitalization (frequency) receives a +1 while the other receives -1.*

The test statistic is based on the sum of these scores and will be stratified by TTR genotype (variant and wild-type) and NYHA baseline classification (NYHA Classes I and II combined and NYHA Class III) resulting in a total of 4 strata (2 x 2).

The term “censored” refers to a subject who discontinues from the trial for reasons other than death. For such subjects, there will be additional follow-up to obtain vital status (and transplant status / cardiac mechanical assist device status) at Month 30 and that information will be used in the analysis. In the case where one subject is censored before a second subject has died, and where the vital status of the first patient at Month 30 is missing, then the frequency of cardiovascular-related hospitalizations at the shorter of their follow-up times (the shorter of the 2 subjects’ study participation) will be used in assigning a +1 or -1. In the simpler case where one subject drops out but both are known to be alive at Month 30, the frequency of cardiovascular-related hospitalizations, at the shorter of their follow-up times (the shorter of the 2 subjects study participation), will be used in assigning a +1 or -1. Comparisons of cardiovascular related hospitalization frequency for subjects who completed all 30 months study duration will be based on the earlier of the two actual study durations (days).

Subjects, who discontinue for transplantation (ie, heart transplantation and combined heart and liver transplantation) or for implantation of a cardiac mechanical assist device, will be handled in the primary analysis in the same manner as death. More specifically, the time of the transplant or cardiac mechanical assist device implant will be used in the subject-to-subject comparison in the same manner as if the subject had died at that time (regardless of any additional vital status follow-up information). Data from subjects who drop out for a liver-only transplantation will be handled in the same manner as the data from all other censored subjects.

The proposed test is a score test based on the sum of the scores for the treated group. A value of $D_i = 1$ for subjects in tafamidis and $D_i = 0$ for subjects in the placebo group. Using the u_{ij} for every pair of subjects defined above, we assign a score to each subject.

The subjects are divided into 4 strata $k = 1; 2; 3, 4$. If A_k is the set of indices of the n_k subjects in the k^{th} strata and that U_i is calculated within strata (for $i \in A_k; U_i = \sum_{j \in A_k} u_{ij}$), then the test statistic is based on

$$T = \sum_k \sum_{i \in A_k} D_i U_i$$

Let m_k be the total number of subjects in the k_{th} stratum who are in the tafamidis group. Then in k_{th} strata

$$E(D_i) = m_k/n_k \text{ and}$$

$$\text{cov}(D_i, D_j) = \frac{m_k(n_k - m_k)}{(n_k - 1)n_k} (\delta_{ij}n_k - 1),$$

where δ_{ij} is the Kronecker delta (valued as 1 if $i=j$ and 0 otherwise).

Since $\sum_{i \in A_k} U_i = \mathbf{0}$ this implies that the mean of T is zero and its variance is

$$V = \sum_k \frac{m_k(n_k - m_k)}{n_k(n_k - 1)} (\sum_{i \in A_k} U_i^2).$$

The hypothesis of interest is tested by comparing T/\sqrt{V} to the normal distribution.

In the event there is insufficient information for the adjudication process to classify either a mortality or hospitalization as cardiovascular related or not cardiovascular related, then the event will be classified as “indeterminate”. In the adjudication process, cases with at least some information indicating a contributory cardiovascular cause, including ambiguous cases, will be adjudicated to the cardiovascular-related category. The test statistic for the “by TTR Genotypes” subgroup analysis will be stratified by NYHA baseline classification (NYHA Classes I and II combined and NYHA Class III). The test statistic for the “by NYHA classifications” subgroup analysis will be stratified by TTR Genotype (variant and wild-type). Subjects who were incorrectly classified during randomization (wrong TTR Genotype or NYHA baseline classification) will be analyzed using the correct TTR Genotype or NYHA baseline classification values.

